HPV31/33/35/39/45/51/52/53/56/58/59/66/68 for exploratory aims. Participants positive for high-risk HPV and/or HPV6/11 on any sample will have a 6-12 month follow-up visit to measure HPV type-specific persistence - a surrogate endpoint recommended by the WHO (87). At young ages, the risk of precancer is very low, but for safety purposes, participants will be offered colposcopy if they have a persistent high-risk HPV cervical infection and anoscopy if they have a persistent HPV16/18 anal infection. Main outcomes will be prevalence and 6-12 month type-specific persistence of cervicovaginal (as an excellent proxy for cervical sampling (87)), anal, and/or oral infections by HPV6/11/16/18 as well as antibody titers for HPV6/11/16/18. Cervical and anal biopsy specimens diagnosed as CIN2+ or AIN2+, respectively, will also be tested for the 15 high-risk and 2 low-risk HPV types for secondary outcomes. In an exploratory aim, we will examine risk factors, including the cervicovaginal microbiome (88), for HPV type-specific persistence in WLWH and HIV[-] women.

At enrollment, blood will be collected for plasma from all participants. In the study laboratory, a stratified random sample of specimens will be selected to measure by ELISA anti-HPV16 and -HPV18 antibody titers and compare HPV-vaccinated WLWH. We will test titers in at least 1,302 samples ($n \geq 548$, 50% with three doses and 50% with two doses of Gardasil®, for both HPV-vaccinated WLWH and for HPV-vaccinated HIV[-] women; $n \geq 108$ for both HPV-vaccinated WLWH and for HPV-vaccinated HIV[-] women as controls) and up to 3,028 samples.

VI.B. Study Locations

In Kigali, the study staff will work with five public clinics that participate in the International Epidemiology Databases to Evaluate AIDS (IeDEA) program and the WE-ACTx private clinic (**Table 2**). Study investigators and staff successfully worked with these clinics in a cervical cancer screening study of 5,000 WLWH (83). If needed, the staff will work with up to four other public health clinics to recruit additional participants.

Table 2. Study enrollment sites	
IeDEA Sites	Non-IeDEA sites
1. Busanza health center (HC)	1. Cor-unum HC

2. Gikondo HC 3. Kicukiro HC 4. Nyarugunga HC 5. Rwanda Military Hospital 6. WE-ACTx private clinic	2. Kacyiru HC 3. Remera HC 4. Rwampara HC
---	---

VI.C. Target Population

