There are no management guidelines or evidence-based intervention for type-specific persistent HPV. Therefore, participants will not receive any clinical intervention for type-specific persistent oral HPV.

VI.G.4. Study Exit

Other participants, including WLWH and/or those with persistent low-risk HPV6- or HPV11 infection, will exit the study.

VI.H. Biospecimen Processing, Storage, and Shipment

The study lab will process, store and test for HPV in oral specimens in saline solution, dry samples, blood samples and FFPE tissue specimens. All specimens will be tested for individual 17 HPV types using the AmpFire HPV genotyping test.

In preparation for testing, oral specimens will be aliquoted, the dry sample will be rinsed into a vial with lysis buffer and FFPE tissue specimens will be suspended in lysis buffer. Specimens will be processed according to manufacturer's instructions. All residual lysed specimens will be stored at the study lab at -80°C for later testing. Select samples will be sent to study collaborators' laboratory for microbiome testing. Additional microbiome testing will be conducted at the study lab.

Whole blood specimens will be processed to obtain aliquots of plasma. Following the protocol established by the Frederick National Laboratory of Cancer Research (FNLCR) HPV Serology Laboratory, select plasma specimens will be sent to FNLCR for testing and others will be tested at the study lab (**Section V.I.2**). After ELISA testing, residual plasma will also be stored at the study lab for later testing.

A biospecimen bank containing residual material from samples collected will be established at the study lab for subsequent methodologic and etiologic research.

VI.I. Laboratory Testing

VI.I.1. AmpFire HPV Testing

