For HPV genotyping of cervicovaginal, anal, and oral specimens for Specific Aim 1 (**Section VII.A**), we will use the AmpFire HPV genotyping test (Genotyping High Risk HPV Real Time Fluorescent Detection; Atila Biosystems, Mountain View, CA, USA), which uses real-time PCR to detect 15 individual HPV genotypes HPV16, 18, 31, 33, 35, 39, 45, 51, 52, 53, 56, 58, 59, 66 and 68, plus low-risk HPV6 and 11, in 5 assay reactions previously established at the study lab and validated against other commercially available assays at RMH (93-96). This method requires no transport buffer (dry specimens) and no DNA purification step and is well suited to be run in clinic settings by personnel with relatively minimal training. For oral specimens in saline solution, specimens will first be spun in the centrifuge to enrich the sample. The AmpFire system provides results for each type within 1.5 hours. Atila has agreed to provide a separate detection tube for the combined detection of HPV6 and 11 (HPV6/11) for this study. The assay will be run per the manufacturer's instructions. The residual lysed specimen will be neutralized according to the manufacturer's protocol using its buffer and stored at -20°C for long term storage and later testing.

FFPE tissues diagnosed as CIN2+ or AIN2+ will similarly have HPV genotyping using the AmpFire system according to the manufacturer's protocol.

For monitoring of quality of Ampfire testing, aliquots of selected samples will be sent to an independent lab for testing with a validated HPV typing assay. The results will be compared with local tests results for quality control and not clinical management. In some cases of negative Ampfire and the positive QC test, participants be referred for follow-up visit. Treatment will not be determined by the QC result.

VI.I.2. HPV Antibody Titors

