All histopathology slides will be scanned at the study lab and reviewed by two local pathologists and the Einstein study pathologist (105). If the diagnoses are concordant, no further review of the case will be performed. If the diagnosis is discordant and at least one pathologist diagnoses CIN2+, the biopsy slide will be subjected to a joint review and consensus diagnosis. For Negative/cervical intraepithelial neoplasia grade 1 pairs of diagnoses, which does not influence our analyses or the care of the participants, there will be no joint review.

VII. STATISTICAL SECTION

VII.A. Specific Aim 1

To measure population effectiveness of prophylactic HPV vaccine in reducing cervicovaginal, anal, and/or oral prevalent and persistent infections by HPV6/11/16/18.

VII.A.1. Analyses.

We will calculate the point prevalence and the prevalence of persisting infection by individual HPV-type specific infections, with binomial 95% confidence intervals (95% CI), for each anatomic and for the woman (all anatomic sites) for Gardasil®-vaccinated WLWH, Gardasil®-vaccinated HIV[-] women, unvaccinated WLWH and unvaccinated HIV[-] women. We likewise will calculate the point prevalence and the prevalence of persisting infection with 95%CI for all

HPV types in aggregate and in sub-groups of HPV types according to the protection afforded by Gardasil®: Gardasil®-targeted types (HPV6, 11, 16, and 18), Gardasil®-untargeted types for which there might be cross-protection (HPV31, 33, and 45) (40, 106, 107), and Gardasil®-untargeted HPV types for which there is little or no evidence of cross-protection (HPV35, 39, 51, 52, 53, 56, 58, 59, 66, and 68). Results will be stratified by age and number of doses (3 vs. 2) as well as other factors possibly associated with HPV prevalence. Differences in the prevalence of these HPV type sub-groups (targeted, possible cross-protection, and untargeted) between the four study groups of women will be tested using Fisher's exact or Pearson chi-square test. Differences in the prevalence of these HPV type subgroups by age, number of doses (3 vs. 2), and other factors within the group, will be tested for statistical significance ($p<0.05$) using a Fisher's exact or Pearson chi-square test.

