Notably, the study groups of participants are fundamentally different populations (vs. a randomized control trial that would recruit from the same population and, as result of randomization, enroll similar, representative populations in each arm). Specifically, there are known differences in age (and therefore possible differences sexual behaviors) between Gardasil®-vaccinated vs. -unvaccinated WLWH, and possible differences in sexual behaviors between Gardasil®-vaccinated WLWH vs. HIV[-] women (since HIV infection predominately is sexually transmitted in this population). Therefore, we will use a relative measure of effectiveness to account for the differences in age and possible differences in exposure to HPV. We will use logistic regression to calculate the odds ratio (OR) of the point prevalence and the prevalence of persisting HPV infections of Gardasil®-targeted HPV types, individually (HPV6, 11, 16, or 18) and in aggregate (HPV6, 11, 16, and 18), vs. untargeted HPV genotypes for which there is no evidence of cross-protection, for each anatomic site individually (cervix, anus, OR oral cavity) and combined (cervix, anus, AND oral cavity). That is, we will compare the ratio between study groups of participants as follows:

$\frac{N_{HPV6/11/16/18}}{N_{HPV35/39/51/52/53/56/58/59/66/68}}$ [vaccinated WLWH] (Group 1)
 $\frac{N_{HPV6/11/16/18}}{N_{HPV35/39/51/52/53/56/58/59/66/68}}$ [unvaccinated WLWH] (Group 2)
 or

$\frac{N_{HPV6/11/16/18}}{N_{HPV35/39/51/52/53/56/58/59/66/68}}$ [vaccinated WLWH] (Group 1)
 $\frac{N_{HPV6/11/16/18}}{N_{HPV35/39/51/52/53/56/58/59/66/68}}$ [vaccinated HIV[-] women] (Group 3)

or

$\frac{N_{HPV6/11/16/18}}{N_{HPV35/39/51/52/53/56/58/59/66/68}}$ [vaccinated HIV[-] women] (Group 3)
 $\frac{N_{HPV6/11/16/18}}{N_{HPV35/39/51/52/53/56/58/59/66/68}}$ [unvaccinated HIV[-] women] (Group 4)

This will allow us to account for differences in HPV exposure, prevalence, and persistence due to differences in age (n.b., prevalence equals incidence * duration; prevalent infections at older ages tend to be more persistent ((108)) and sexual behaviors between groups. Additional logistic regression models may be used to adjust specifically on other factors, including age, number of doses, and sexual behaviors, to account for population differences between study groups.

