Similarly, exploratory analyses will compare the effectiveness of HPV vaccination for cross-protection types and endpoints of cumulative detection of Gardasil®-targeted HPV types-associated CIN2+ and/or anal intraepithelial neoplasia grade 2 or more severe (AIN2+) (vs. untargeted HPV type-associated CIN2+ and/or AIN2+) between study groups.

For participants in the existing IeDEA database we will extract HIV specific variables. For those who we cannot match to the IeDEA database, will extract HIV specific variables from medical records.

In another exploratory analysis, among WLWH, the presumed route of HIV acquisition (either maternal to child or behavioral) will be compared with HPV positivity and, among HPV-positive women, HPV viral load.

VII.A.2. Sample Size/Power for Gardasil®-vaccinated vs. unvaccinated WLWH.

For this analysis, we will make the following assumptions: 1) at least 30% prevalence of HPV infection (of any anatomic site) at baseline, 25% of which will be Gardasil®-target HPV types and 55% will be untargeted HPV types, 2) a 10% loss to follow-up (LTFU) in at follow up visit, and 3) at least 70% of HPV infections persist for 6-12 months. We justify an HPV prevalence of at least 30% based on 30% prevalence of high-risk HPV infection of the cervix in 30-year-old WLWH from our previous U54 study (109). We expect that the HPV prevalence may be higher since the prevalence of HPV, like that of other sexually transmitted infections, tends to peak about 5 years after the median age of sexual initiation in a population. However, we conservatively used 30% to ensure adequate statistical power. We justify our assumption of a maximum of 10% follow-up, given our experience working in Rwanda over the last ~20 years. We justify 70% of prevalent HPV infections persisting for 6-12 months, given that 36-50% of prevalent HPV infections persist 6-months in HIV[-] women (109, 110) and WLWH have an impaired immunity to HPV (8, 9).

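### Does a combined HPV6/11 detection tube make the separate HPV6 and HPV11 analyses in VII.A.1 impossible?

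*Combined protocol and SAP*

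**What the plan says.** Section VI.I.1 describes the AmpFire assay, "which uses real-time PCR to detect 15 individual HPV genotypes", adds HPV6 and HPV11, and places the whole panel in 5 reactions. Of the system it says: "The AmpFire system provides results for each type within 1.5 hours". The next sentence reads: "Atila has agreed to provide a separate detection tube for the combined detection of HPV6 and 11 (HPV6/11) for this study".

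Other sections treat the two low-risk types as distinct results:

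- VI.H: "All specimens will be tested for individual 17 HPV types using the AmpFire HPV genotyping test".
- VII.A.1, descriptive part: "We will calculate the point prevalence and the prevalence of persisting infection by individual HPV-type specific infections".
- VII.A.1, logistic regression: odds ratios for the targeted types "individually (HPV6, 11, 16, or 18) and in aggregate (HPV6, 11, 16, and 18", each against the untargeted types.
- VI.A: "Main outcomes will be prevalence and 6-12 month type-specific persistence of cervicovaginal", anal and oral infection.

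No section says whether the extra tube returns one signal or two, and no routine second assay is planned to separate an HPV6/11-positive result. The independent-laboratory typing in VI.I.1 covers selected samples, for quality control only.

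**The concern.** In VI.I.1 the word individual is attached to the 15 high-risk types, while HPV6 and HPV11 get a special tube described as combined. Read literally, that suggests one pooled signal: 15 + 1 = 16 distinguishable results, where VI.H needs 15 + 2 = 17.

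Three things would then follow:

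- The separate HPV6 and HPV11 prevalence, persistence and odds ratios, two of the four per-type analyses named in VII.A.1, could not be produced from the assay.
- A woman who cleared HPV6 and carried HPV11 at follow-up, or the reverse, would be scored as persistent, although the main outcome is type-specific.
- If the ratios in VII.A.1 count infections rather than women, an HPV6 and HPV11 co-infection would count once.

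**Working it through.** **Is pooling established?** The plan gives no figure to reproduce here, so the first check compares the text.

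- Fifteen individually reported types in at most 5 reactions means at least one tube carries 15/5 = 3 or more types that are told apart. Sharing a tube therefore does not imply pooling on this platform.
- The sentence just before the one on the combined tube promises a result per type.
- The slash label proves nothing. Section I.B uses the same shorthand for HPV16/18, which are typed separately.
- VI.F.2 refers to 17 genotypes, and VI.A to 15 high-risk and 2 low-risk types.

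Two signals from one tube is therefore a plausible reading, and the documents do not decide between the two.

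**If the signal is pooled, how much changes in WLWH?**

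Inputs from VII.A.2: 757 per group, 30% HPV prevalence, "25% of which will be Gardasil®-target HPV types and 55% will be untargeted HPV types", 10% loss to follow-up, 70% persistence.

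- Targeted infections per group: 757 × 0.30 × 0.25 = 56.8
- Seen at follow-up: 56.8 × 0.90 = 51.1
- Persistent: 51.1 × 0.70 = 35.8

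Assumptions not in the documents: HPV6/11 make up 25% to 50% of targeted infections, and 5% to 10% of those that clear show the other type at follow-up.

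- Falsely persistent, low: 51.1 × 0.25 × 0.30 × 0.05 = 0.19 women (0.19/35.8 = 0.5%)
- Falsely persistent, high: 51.1 × 0.50 × 0.30 × 0.10 = 0.77 women (0.77/35.8 = 2.1%)

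Take a true odds ratio of 0.50 with equal comparator counts. The vaccinated group then has 35.8/2 = 17.9 persistent infections and half the targeted infections at risk of switching, so at most 0.77/2 = 0.38 false cases.

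| False cases fall in | Calculation | Observed OR |
|---|---|---|
| Both groups, same switching rate | (17.9 + 0.38)/(35.8 + 0.77) | 0.50 |
| Vaccinated only | (17.9 + 0.38)/35.8 | 0.51 |
| Unvaccinated only | 17.9/(35.8 + 0.77) | 0.49 |

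**HIV-negative groups.** Assume the same 30% and 25%, with the 36% to 50% persistence that VII.A.2 cites for HIV-negative women. False cases per group run from 51.1 × 0.25 × 0.50 × 0.05 = 0.32 to 51.1 × 0.50 × 0.64 × 0.10 = 1.64. At 36% persistence there are 51.1 × 0.36 = 18.4 persistent infections. Equal switching rates again leave 0.50. The one-sided extremes are (9.2 + 0.82)/18.4 = 0.54 and 9.2/(18.4 + 1.64) = 0.46.

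**What could the separate HPV6 and HPV11 odds ratios show with any assay?** Persistent HPV6/11 in unvaccinated WLWH: 35.8 × 0.25 = 9 to 35.8 × 0.50 = 18. At the upper end, split evenly, that is 9 per type. A true OR of 0.50 gives 4.5 in the vaccinated group. Untargeted persistent infections: 757 × 0.30 × 0.90 × 0.70 × 0.55 = 78.7. Treating the counts as independent:

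SE(log OR) = √(1/4.5 + 1/9 + 2/78.7) = 0.60

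95% interval: 0.50 × exp(±1.96 × 0.60), about 0.15 to 1.6.

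These estimates are descriptive even with perfect typing.

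**The case for a change.** The strongest case for changing the plan does not rest on bias. The sentence on a result for each type describes the system in general, whereas the following one describes a tube made for this study and labels its output HPV6/11. A laboratory and an analyst could code that variable differently. If it is pooled, named analyses cannot be delivered as written, and HPV6/11 persistence stops being type-specific. Retyping would need retained material, and VI.F.1.d says residual oral specimens are discarded after testing.

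Part of this stands. The wording is ambiguous, only the manufacturer or the assay output can resolve it, and a clarifying phrase in VI.I.1 would do no harm. The rest carries less weight:

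- Analysts will see one HPV6/11 column or two as soon as results arrive. With one column, reporting HPV6/11 as a single category is the obvious course and involves no choice that could favour a result.
- The loss need not be permanent. VI.H and VI.I.1 store residual lysates, and VI.F.1.d keeps oral aliquots. On the same assumed shares, 56.8 × 0.25 = 14 to 56.8 × 0.50 = 28 women per group would need retyping, but that extra laboratory step would serve only estimates too imprecise to matter.
- An added HPV16/18-only version of the main odds ratio would gain little, because VII.A.1 already plans separate HPV16 and HPV18 odds ratios, which pooling cannot touch.

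**Conclusion.** No change to the plan follows. The inconsistency between VI.I.1 and VI.H/VII.A.1 is real as a matter of wording, but pooling is not shown, and the text on the assay leaves two separate signals plausible.

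If the signal is pooled, the separate HPV6 and HPV11 estimates are lost unless stored material is retyped, and HPV6/11 persistence becomes persistence of a combined signal. The aggregate odds ratio, which is the one VII.A.2 powers, would move by about 0.01 at most in WLWH, and not at all if switching is equally common in both groups. The HIV-negative comparison could move by up to 0.04, and only if every switch fell in one group. These sizes rest on the assumed 25% to 50% share and 5% to 10% switching rate. Per-woman aggregate prevalence, the HPV16 and HPV18 results, the trigger for the follow-up visit and the 757 per group hold under either reading, and no management step in VI.G depends on telling HPV6 from HPV11.

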For Specific Aim 2 (**Section VII.B**) anti-HPV16 and HPV18 IgG antibody titers will be measured from plasma by an ELISA based on a previously described method (97, 98) and according to the protocol established by the FNLCR HPV Serology Laboratory (99). Only anti-HPV16 and HPV18 IgG antibody titers, and not titers for all 4 HPV types, will be evaluated as antibody titers are correlated between antibody responses for the different types. HPV16 and HPV18 are the two most important HPV types and cause approximately 70% of cervical cancers (19). HPV16 tends to induce the highest titers while HPV18 tends to induce the lowest titers among the 4 types (100, 101) and therefore measuring the two types gives us a range in responses while using study resources cost effectively. The FNLCR Serology Laboratory will teach the ELISA protocol to [name] (co-I; Einstein), who will oversee the transfer of this ELISA assay to the study lab in Rwanda.

First, 20% of each group will be run at the Frederick NCI lab, then the results will be replicated at the study lab (masked to the original results), and then the remaining 80% of the testing will be finished at the study lab. As an additional quality control measure, a 10% random sample of specimens will be re-run at the NCI Frederick lab (masked to the original results) (inter-laboratory reliability) and another 10% random sample of specimens at the study lab (intra-laboratory reliability). The study lab will achieve at least 90% correlation for both anti-HPV16 and -HPV18 titers with FNLCR Serology Laboratory on the first 20% of specimens tested before the study lab embarks on testing the last 80% of specimens (101). Positive (e.g., IS standards (102, 103)) and negative controls (e.g., negative plasma) will be included in some testing plates to monitor assay performance per WHO recommendations (104).

VI.I.3. CVM Analyses

Baseline and follow-up specimens collected for baseline HPV-positive participants will be tested for cervicovaginal microbiota by next-generation sequencing (NGS) for our Exploratory Aim (**Section VII.C.**) on short-term HPV persistence. The first 20% of specimens will be tested in both the collaborating lab and the study lab until acceptable agreement is achieved (see below) after which the remaining 80% of specimens will be tested at the study lab with retesting 10% for quality control.

VI.I.4. Pathology

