Sample size calculation relates to the relative effectiveness measure as discussed. Under above assumptions, a sample size of 757 vaccinated and 757 unvaccinated WLWH will provide $\geq 80\%$ power ($p=0.05$) to detect an OR of ≤ 0.5 for 6-12 month persistent HPV6/11/16/18 infections, relative to HPV35/39/51/52/53/56/58/59/66/68 (but not HPV31/33/45 because of possible cross protection), in Gardasil®-vaccinated vs. -unvaccinated WLWH. Consequently, because there will be more participants with a prevalent infection than 6-12 month persistent HPV infection (because there are no losses to follow-up or HPV viral clearance for which to account), there will

be $\geq 80\%$ power ($p=0.05$) to detect a OR of ≤ 0.75 in point prevalence of HPV6/11/16/18 infection relative to HPV35/39/51/52/53/56/58/59/66/68, in Gardasil®-vaccinated vs. - unvaccinated WLWH.

VII.B. Specific Aim 2

To quantify, and examine the determinants of, long-term antibody responses to, HPV vaccination.

VII.B.1. Analyses.

Geometric mean titers (GMT) and seropositivity (seroconversion) will be compared between 1) HPV-vaccinated WLWH and HPV-vaccinated HIV[-] women, overall and stratified on the number of vaccine doses, 2) HPV-vaccinated and unvaccinated WLWH, overall and by the number of doses received by the HPV-vaccinated WLWH, and 3) three vs. two doses for HPV-vaccinated WLWH and 4) HPV-vaccinated and unvaccinated HIV[-] women, overall and by the number of doses received by the HPV-vaccinated HIV[-] women.

Differences in GMT and seropositivity will be tested for statistical significance using the Mann-Whitney and Fisher's exact tests, respectively. ANOVA and logistic regression models will be used to adjust for/assess the association of other factors (e.g., age at vaccination, age at enrollment into the study, number of doses, HIV status [positive vs. negative and current antiretroviral therapy, CD4 counts, and HIV viral load] and history [e.g., CD4 nadir], and detection of HPV genotypes, etc.) with GMT and seropositivity, respectively.

Among vaccinated and unvaccinated HPV seropositive WLWH, the association between HPV antibody titer and presumed route of HIV acquisition (either maternal to child or behavioral) will be examined.

VII.B.2 Sample Size/Power to compare Gardasil®-vaccinated WLWH vs. Gardasil®-vaccinated HIV[-] women.

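### The ELISA transfer gate of at least 90% correlation, as ordinarily read, cannot see a constant shift between laboratories: absolute GMTs, and seropositivity if the cut-off is carried over, are exposed, while between-group GMT ratios are not

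*Combined protocol and SAP*

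**What the plan says.** Section VI.I.2 (HPV Antibody Titers) stages the transfer of the anti-HPV16 and anti-HPV18 ELISA. "First, 20% of each group will be run at the Frederick NCI lab", and the study laboratory repeats those specimens masked. The pass rule is "The study lab will achieve at least 90% correlation for both anti-HPV16 and -HPV18 titers" with FNLCR "on the first 20% of specimens tested before the study lab embarks on testing the last 80% of specimens". The section does not say which coefficient is meant, whether it is taken on raw or log titres, or whether it is computed within groups or across them.

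The same section adds three further checks: a masked 10% re-run at the reference laboratory, a 10% re-run at the study laboratory, and international standards plus negative controls on some plates. None has an acceptance limit or a stated action on failure.

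Section VII.B.1 uses the results in two ways: GMTs and "seropositivity (seroconversion) will be compared" between groups, by Mann-Whitney and Fisher's exact tests respectively. One planned contrast is "HPV-vaccinated and unvaccinated WLWH, overall and by the number of doses received by the HPV-vaccinated WLWH". Neither section gives a seropositivity cut-off. No section says which laboratory's value is analysed for the doubly tested 20%, and Section VI.H leaves open a dataset that mixes the two laboratories.

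**The concern.** Correlation measures whether two laboratories rank and space specimens alike, not whether they report the same titre. A calibration error that multiplies every study-laboratory titre by the same factor is an obvious way for a transfer to fail, and a product-moment or rank correlation does not respond to it. A mis-calibrated assay could therefore meet the only numeric condition and go on to produce the remaining 80% of results.

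At stake are quantities read on an absolute scale:

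- The GMTs themselves.
- Seropositivity, if the cut-off comes from the reference laboratory.
- The Section VII.B.1 analysis of titre by route of HIV acquisition, which is restricted to seropositive women, so the cut-off decides who enters it.
- The later work on durability of immunogenicity that Section XI hopes for, which would need titres stable in absolute terms.

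A second, lesser weakness is that the transfer sample takes 20% of every group. A coefficient computed across groups partly measures the gap between high- and low-titre groups rather than agreement among vaccinated women.

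**Working it through.** The 90% limit is a chosen criterion, so there is no derivation to reproduce. The related figure that can be checked is the Aim 2 power, which supplies the missing SD.

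**1. SD of log titre (back-solved, since Section VII.B.2 only cites it).** With 274 per group, 80% power and two-sided 0.05 (two-sided assumed), SD = d × √(274/2) / 2.80.
- 30% lower: d = ln(1/0.70) = 0.357, SD = 1.49.
- 30% higher: d = ln(1.30) = 0.262, SD = 1.10.

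At 548 per group, SD 1.49 gives a detectable difference of 22.3% lower, against the stated 22%; SD 1.10 gives 20.4% higher. The range 1.10-1.49 is used below.

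**2. Transfer sample.** Section VI.A lists 548 + 548 + 108 + 108 = 1,312 specimens (it states at least 1,302). Twenty per cent is about 262 pairs: about 219 from the main vaccinated groups and 43 controls. The text describes the controls as "for both HPV-vaccinated WLWH and for HPV-vaccinated HIV[-] women as controls". They are taken here as unvaccinated because Section VII.B.1 compares vaccinated with unvaccinated women. That is an assumption.

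**3. Shift.** On the log scale, study = reference + ln(s) + noise. Adding a constant leaves the correlation unchanged; simulated values were identical for s = 0.5, 0.7, 1, 1.5 and 2. Lin's concordance does respond: with equal variances V in both laboratories it is r / [1 + (ln s)²/(2V)]. With an assumed within-group r of 0.92 and a 10-fold gap between vaccinated women and controls:

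| s | Correlation | Pooled concordance |
|---|---|---|
| 1 | 0.940-0.950 | 0.940-0.950 |
| 0.7 | 0.940-0.950 | 0.920 |
| 0.5 | 0.940-0.950 | 0.845-0.869 |

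A pooled concordance limit of 0.90 would catch the 2-fold shift but pass the 30% one.

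**4. Mixing.** Pooled r = (r_w·SD² + B)/(SD² + B), where B = p(1 − p)D², p = 216/1,312 and D = ln(fold gap). The within-group r_w that gives a pooled 0.90 is:

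| Assumed gap | r_w needed |
|---|---|
| 5-fold | 0.87-0.88 |
| 10-fold | 0.84-0.87 |
| 20-fold | 0.80-0.84 |
| 50-fold | 0.73-0.81 |

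**5. Effect of a 2-fold low assay (s = 0.5).**
- Absolute GMT: 0.50 of true, or 0.5^0.8 = 0.57 if the first 20% keep reference values.
- GMT ratio between groups: a true 0.70 stays 0.70. If both laboratories' values are mixed at 20/80 in each group, power at 274 falls from 80% to 78-79%.
- Seropositivity with a carried-over cut-off: Φ(z − ln 2/SD). An assumed 95% becomes 84-88%, and an assumed 84% becomes 64-70%. A group with GMT at the cut-off goes from 50% to 26-32%. One with GMT 20 times the cut-off goes only from 98-99.7% to 94-98%.
- Difference in seropositivity, assuming 95% in HIV-negative women and a GMT 30% lower in WLWH: 3.0-4.3 points with no shift, 5.4-9.0 points if the assay is 2-fold low, 1.3-1.4 points if 2-fold high.

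**6. Precision available for a ratio limit.** With r = 0.90, the SD of the paired log difference is SD × √0.2 = 0.49-0.67. The 95% CI of the geometric mean ratio is ×/÷ exp(1.96 × that/√n):
- 219 vaccinated pairs: 1.07-1.09.
- 131 pairs (the 10% re-run): 1.09-1.12.
- 43 control pairs, same SD and r assumed: 1.16-1.22.

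**The case against.** The strongest reply is that the main comparison is safe, and that is correct. Section VII.B.2 powers only GMT differences. A constant factor cancels in the ratio and leaves ranks unchanged, and taking 20% of every group keeps laboratories balanced across groups. A reader might infer that the gate puts the powered Aim 2 result at risk; the documents do not support that.

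A reader might also infer that a shift would manufacture or hide seropositivity differences. The same shift applies to every group, so it does not create a difference where none exists; it can enlarge or shrink a real one. Even that needs a cut-off carried over from the reference laboratory. If the study laboratory sets its own, for example from negative plasma, a constant factor cancels. The plan does not say which applies.

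Three more points stand. Correlation is undefined, and an intraclass or concordance coefficient would react to a shift. Pooling across groups is an inference, and so is the unvaccinated status of the controls. The masked re-run and the standards could well expose a shift, so it would be wrong to say that bias must go unnoticed. What these checks lack is a limit, an action and any role in releasing the remaining 80%.

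Finally, mixing hides noise rather than bias, and with about 16% controls its effect is modest unless the titre gap is large.

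**Conclusion.** The concern holds in a limited form. Read in the ordinary way, the only numeric transfer gate is blind to a constant shift, and it is lenient on noise if computed across groups. A mis-calibrated assay could meet it as written. The consequence falls on absolute GMTs and, with a cut-off fixed on the reference scale, on seropositivity and the size of its group differences. For a 2-fold low assay it ranges from a few points in groups far above the cut-off to about 18-24 points in a group at the cut-off (50% to 26-32%). Between-group GMT ratios and the Mann-Whitney test are not biased.

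The shift size, titre gap, cut-off position and baseline seropositivity are assumptions, because the documents give none. The SD is back-solved. This is an inexpensive improvement to make before the transfer starts, not a flaw in the powered comparison.

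**What to change.** In Section VI.I.2, keep the correlation condition but name the coefficient and compute it on log titres. Then add, using the duplicate specimens already planned and separately for each antigen:

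- A prespecified limit on the study-laboratory/FNLCR geometric mean ratio among vaccinated women, for example a 95% CI within 0.80-1.25, with the margin justified by the sponsor. At ×/÷1.07-1.09 this is attainable, and shifts of 0.7 or 0.5 would fail it. Concordance alone is not enough, given the 30% shift it would pass.
- The same ratio checked in the low-titre controls. With about 43 pairs the interval is too wide to serve comfortably as a pass rule at that margin.
- Within-group concordance and agreement on seropositivity, reported with the cut-off and the scale on which it is set.
- The same ratio limit, with a stated action, for the 10% inter-laboratory re-run.

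In Section VII.B.1, state that study-laboratory values are used for all specimens, since the first 20% are repeated there anyway.

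No extra assays are needed. The added limit is a stricter rule than the present one, so the transfer may be delayed for recalibration if bias is found.
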